10. STATISTICAL DESIGN

A formal Statistical Analysis Plan (SAP) (also referenced to as the Statistical Considerations) will be written and finalized prior to the trial commencing subject recruitment. The SAP will detail the summaries and analyses to be performed.

Smith & Nephew Wound Management Global Medical and Clinical Affairs Department will conduct data management and statistical analysis. Unless otherwise stated, all significance tests and hypothesis testing will be two-sided, performed at the 5% significance level. Resulting P-values will be quoted and 95% two-sided confidence intervals will be generated where appropriate. All analyses will be performed in SAS v9.4 (or later).

Where data summaries are specified, categorical and ordinal variables will be summarized using frequency distributions which will detail the number and percentage of subjects which fall into each category. Continuous variables will be summarized using the following summary statistics: mean, median, standard deviation, minimum and maximum values, and number of observations.

For purposes of analysis, unless otherwise stated, treatment refers to either PICO or tNPWT. All data for individual negative pressure wound therapy devices used during the study will be pooled to constitute the tNPWT treatment arm. Where specified, additional summaries and analysis will be performed on individual tNPWT devices in addition to the overall tNPWT treatment arm.

10.1 EVALUABILITY

All subjects that are randomized at Study Visit 1 (baseline visit) are considered study participants. The following study populations and analysis sets will be defined:

Safety Population: This will include all subjects that are randomized to, and receive, one of the trial treatments.

Full Analysis Set: Using the Intent-to-treat (ITT) principle, this will include all subjects that are randomized and receive trial treatment, and attend at least one follow-up post baseline. Subjects will be analyzed according to treatment randomization.

Per Protocol Population (PP): This will include all subjects that are randomized to trial treatment, meet the inclusion/exclusion criteria, do not discontinue trial treatment within the first nine (9) weeks (- 1 day) and have no significant protocol deviations including the use of an unapproved tNPWT device as defined in the protocol. Subjects that achieve closure will be included regardless of time on therapy unless they are deemed to have significant protocol deviations or failed to meet the inclusion/exclusion criteria.

Statistical analysis will be performed using each of the subject populations as follows. Analysis of the primary, secondary and exploratory efficacy objectives will be performed separately using both the Full Analysis Set and the Per Protocol Population. All safety analyses will utilize the Safety Population.

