8. STUDY DESIGN

8.1 STUDY DESIGN

This is a multi-center, Phase 4, randomized, open-labelled, comparative-effectiveness study in subjects with at least one lower extremity wound (VLU or DFU). Approximately 160 subjects, including a minimum of 100 subjects presenting with VLU and 46 presenting with DFU, will be randomized to one of two treatment groups in an equal allocation to receive either PICO single-use NPWT system or tNPWT system, for 12 weeks, or until target ulcer closure (by surgical intervention or secondary intention), whichever occurs first.

Subject randomization to trial treatment will be conducted using an online randomization system and will be stratified by the subject's ulcer type and ulcer size (cm²) at baseline. Each stratification factor will contain two levels: Venous Leg Ulcer or Diabetic Foot Ulcer, and Small or Large Ulcer with the definition of small and large dependent on ulcer type. The result will be four possible strata:

- Venous Leg Ulcer $\leq 12\text{cm}^2$ (small)
- Venous Leg Ulcer $> 12\text{cm}^2$ (large)
- Diabetic Foot Ulcer $\leq 2\text{cm}^2$ (small)
- Diabetic Foot Ulcer $> 2\text{cm}^2$ (large)

Further details regarding the randomization process will be provided in the SAP.

An interim analysis will be performed after 80 subjects have completed the study, incorporating a minimum of 40 VLU and 20 DFU.

CONFIDENTIAL DOCUMENT
This document contains confidential information, which is the property of Smith & Nephew, Inc. Do not copy, disclose, or circulate without written authorization from the appropriate Smith & Nephew personnel

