9.2 DISCONTINUED SUBJECTS

Discontinued subjects are those who voluntarily discontinue participation, who are withdrawn for safety reasons or who have missed a sufficient number of study visits, procedures or test article doses, as defined below, to be ineligible for further participation.

All subjects who discontinue the study prior to completing the regularly scheduled visits should complete the End of Treatment Assessment or Early Discontinuation Visit 14.

Any changes in medical health and/or the use of concomitant medications will be captured. If any SAE, target ulcer AE, or DevD were observed since the previous visit, they must be recorded (refer to Section 12, *Adverse Events*, for instructions on reporting and evaluation

procedures). All females of child-bearing potential must also undergo a urine pregnancy test upon exiting the study. Finally, if appropriate, the Investigator will also advise the subject of subsequent therapy and/or procedures necessary for their medical condition.

During the course of the study, the subject must be discontinued from study treatment in the case of any of the following:

- An infection of the target ulcer occurs and does not respond as expected to appropriate conventional treatment after 2 weeks of therapy
- Progressive disease defined by an increase of $\geq 75\%$ in the ulcer surface area at any time during the treatment phase using the measurement from Run-in Visit 2 as the baseline target ulcer measurement. The increase is calculated as follows:

$$\left[\left(\frac{Area_{V_n} - Area_{RV2}}{Area_{RV2}} \right) \times 100 \right] \geq 75$$

- Persistence of an SAE, device –related AE or abnormal laboratory value that in the opinion of the Investigator places the subject at risk should they continue in the study
- Subject misses > 2 weekly study visits during the treatment period.
- Subject misses 14 consecutive days of therapy or standard care treatment during the treatment period
- Subject misses 21 cumulative days of therapy during the treatment period

Subjects may be discontinued from the study at any time if, in the opinion of the Investigator, their continued participation in the study poses a risk to the subject. Additionally, subjects may be discontinued from the study for the following reasons:

- Adverse device effects
- Lost to follow-up
- Subject decision unrelated to an adverse device effects
- Noncompliance (e.g., did not follow instructions, took disallowed medications)
- Other

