9.4 STUDY METHODS AND MEASUREMENTS

For purposes of derivation of endpoints and subsequent analysis, study treatment refers to either PICO or tNPWT. Four individual negative pressure wound therapy devices are available for use during the study; the data for the study endpoints collected for each of these individual devices will be pooled to constitute the tNPWT treatment arm.

Primary Endpoint

The primary endpoint for this study is the percentage change in target ulcer area over the 12-week treatment period. Target ulcer area is defined as surface area as measured by the ARANZ Silhouette Device (18.2) at each study visit by the Investigator. The percentage change in target ulcer area over the 12-week treatment period is then defined as:

CONFIDENTIAL DOCUMENT
This document contains confidential information, which is the property of Smith & Nephew, Inc. Do not copy, disclose, or circulate without written authorization from the appropriate Smith & Nephew personnel

$$\text{Percentage change in target ulcer area} = \left(\left(\frac{\text{Area}_{SV13} - \text{Area}_{SV1}}{\text{Area}_{SV1}} \right) \times 100 \right)$$

In cases where the target ulcer area is closed in the opinion of the Investigator (regardless of 1-week confirmation), the ulcer area will be imputed as 0 cm², resulting in a percentage change in target ulcer area of 100%. In circumstances where the ulcer area is missing at the Study Visit 13 for subjects that have not withdrawn prematurely due to closure, the last observation carried forward (LOCF) method will be used.

Key Secondary Endpoints

The key secondary endpoints are the percentage change in the target ulcer dimensions not assessed as part of the primary endpoint, namely depth and volume. As defined for the primary endpoint, ulcer depth and volume will be measured by the ARANZ Silhouette Device at each visit by the Investigator, and the percentage change in depth and volume over the 12-week treatment period will then be defined as per the formula above replacing the area measurements with the corresponding depth and volume respectively.

Secondary Endpoints

The secondary endpoints are as follows:

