10.3 EFFICACY ANALYSIS

10.3.1 Primary Efficacy

The primary endpoint of the study is the percentage change in target ulcer area over the 12-week treatment period and will be analyzed as follows. An initial linear regression model will contain covariates for treatment, center, wound type, baseline (defined as Study Visit 1) target ulcer area and duration of target ulcer. For purposes of the primary analysis, any centers with less than 10 subjects will be pooled. A forward selection procedure will be used for the addition of other baseline covariates with an F-value to attain a significance level of 0.1. Further baseline covariates to be assessed as part of this procedure include: subject age, body mass index, baseline ulcer depth, ABI and baseline level of exudate. The resulting primary analysis presented will correspond to the final model from the forward selection procedure. The results for the initial model will also be presented. For each of the effects in the initial and final model, the p-value, parameter estimate and corresponding 95.4% confidence interval will be presented.

Secondary subgroup analyses may be conducted as a result of the covariate analyses. Additionally, treatment will be fitted on its own in a further linear regression model. The potential for interactions, particularly treatment by center interactions will be examined by fitting the required interaction terms in addition to those effects in the final linear regression model from the forward selection procedure.

Non-inferiority will be concluded in each case if the upper bound of the 95.4% confidence interval for the parameter estimate relating to treatment covariate (coded as tNPWT – PICO) is less than ($<$) 12.5 which relates to the desired one-sided test at the 2.5% significance level after adjusting for the interim analysis.

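### The primary non-inferiority set keeps early closures but drops forced early stops for ulcer growth or infection, and the Full Analysis Set has no stated role in the conclusion

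*Protocol*

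**What the plan says.** Protocol 10.3.1 and SAP 4.9 run the primary analysis on PP and repeat it on FAS. If the conclusions differ, the difference is to be looked into. Agreement of both sets is a condition only for moving on to superiority.

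Protocol 10.1 and SAP 4.4 define PP. Members must "do not discontinue trial treatment within the first nine (9) weeks (- 1 day"), must be eligible and must have no significant deviation. The one exception to the nine-week rule is "Subjects that achieve closure will be included regardless of time on therapy". That fits the design, in which treatment runs "for 12 weeks, or until target ulcer closure (by surgical intervention or secondary intention), whichever occurs first".

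Protocol 9.2 lists events after which "the subject must be discontinued from study treatment in the case of any of the following". Two of them are failures of the target ulcer itself:
- "Progressive disease defined by an increase of" 75% or more in area over baseline, at any time in the treatment phase;
- "An infection of the target ulcer occurs and does not respond as expected to appropriate conventional treatment after 2 weeks of therapy".

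Neither is excepted from the nine-week rule. In FAS, given one post-baseline follow-up, these subjects are kept: where the Visit 13 area is missing, "for subjects that have not withdrawn prematurely due to closure, the last observation carried forward (LOCF) method will be used" (Protocol 9.4).

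**The concern.** Before week 9, whether a subject stays in PP depends on how the ulcer did. A closed ulcer stays in at a 100% reduction. An ulcer that grew enough to force a stop goes out. The primary endpoint is ulcer area, so the exclusion is tied to the outcome.

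If the two arms have the same rate and severity of such failures, the difference between arms is not biased. If tNPWT has more, PP works against PICO. If PICO has more, PP can show no difference while FAS shows a deficit at the margin. In that last case the plan shows the disagreement but does not say what is concluded about non-inferiority. The trial is open-label and the sponsor does the analysis, so this is better settled before the data are seen.

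**Working it through.** **The plan's own figures.** Inputs from Protocol 11: margin 12.5, SD 24.5, mean reduction 60%, one-sided cumulative alpha 0.025, interim bounds 2.963 (efficacy) and 0.559 (futility), 20% dropout. A true difference of 0 is implied. A fixed design needs 61 per arm (122). With the two interim bounds at half information, and a final bound of 1.969 chosen so that total alpha is 0.025, 128 subjects give power 0.802. Then 128/0.80 = 160. Both figures reproduce.

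**Excess failures that put FAS at the margin.** The documents give no failure rates, so the following are assumptions. Score reduction as positive and take the deficit as tNPWT − PICO, with all other subjects averaging 60.
- Failures carried forward at +75% growth: 12.5/(60 + 75) = 9.3 percentage points, or 7.4 of 80.
- Failures carried forward at no change: 12.5/60 = 20.8 percentage points, or 16.7 of 80.

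These are two example points, not limits. Growth of 75% is the smallest that forces a stop, so larger growth needs fewer failures. An infection stop after partial healing needs more.

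**Power of PP alone.** If 20% leave PP, 64 per arm remain. SE = 24.5 × √(2/64) = 4.33. The final rule is a 95.4% interval, z = 1.995. Power = Φ(12.5/4.33 − 1.995) = Φ(0.89) ≈ 0.81.

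**Simulation.** Assumptions: 80 randomized per arm; forced stops counted within the 20% leaving PP as far as they fit; other dropouts kept in FAS with the completers' distribution; unadjusted t interval at 95.4%; interim ignored.

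With the FAS deficit set at 12.5:

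| Forced stops falling after week 9 | PP passes |
|---|---|
| none | about 80% |
| a quarter | about 30-45% |
| half | about 10-20% |

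With all stops before week 9, both sets pass in only about 2-3% of trials. Later stops stay in PP, which is why timing matters so much.

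With truly equal arms and all stops before week 9:

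| Failures per arm | PP passes | Both pass | PP passes, FAS fails (by subtraction) |
|---|---|---|---|
| none | 80.6% | 79.2% | 1.4% |
| 5% at no change | 80.7% | 74.3% | 6.4% |
| 2% at +75% | 80.6% | 65.7% | 14.9% |
| 5% at +75% | 80.6% | 49.9% | 30.7% |

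If ordinary dropouts instead carry forward a mean reduction of 40%, both-set power is 77.1%, 72.9%, 64.3% and 49.4%.

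**The sign of the rule.** The formula in Protocol 9.4 and SAP 4.3 is (later area − baseline)/baseline, so a reduction is negative. Protocol 9.4 nevertheless gives closure as 100%. If the formula is taken literally, more failures on PICO push tNPWT − PICO downward, away from an upper limit of 12.5, and a rule on that limit would not catch them.

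**The case against.** **PP is the named primary analysis, so a PP pass settles the matter.** This is the strongest reply, and it is a possible reading. PP is also a conventional choice for non-inferiority. But the plan also runs FAS and promises to look into differing conclusions, without saying whether FAS can alter the non-inferiority conclusion. Requiring both sets is partly a preference, though it is the condition the plan already sets before superiority.

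**The protocol already requires both.** Protocol 10.3.1 says "Non-inferiority will be concluded in each case if the upper bound of the 95.4% confidence interval" meets the margin. Those words follow a list of regression models and come before the populations are discussed. The matching sentence in SAP 4.9 lacks the phrase about each case. It is not a two-set rule.

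**An imbalance would be visible.** This stands. SAP 4.4 lists exclusions with reasons, and FAS is reported. Visibility does not supply the conclusion.

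**The power losses leave the plan's inputs.** This stands too. Failures of 2% or 5% per arm at +75% raise the FAS SD well above the plan's worst case of 24.5, and the documents do not say whether the source studies' SDs already include such failures.

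A reader might go further and infer that the PP definition favors PICO, or that a PP pass at the FAS margin is usual. The documents support neither. They give no failure rates by arm, and the 80% figure needs every forced stop to fall before week 9, although the growth rule applies throughout treatment.

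**Conclusion.** The point holds in a limited form. PP is the primary set, its nine-week exclusion spares closure but not the compelled stops for growth or infection, and FAS has no stated part in the non-inferiority conclusion. Bias arises only if failures differ between arms in rate or severity, and it could run either way. The chance of an unwarranted PP pass depends on rates, carried-forward values and timing that the documents do not give, so the figures above are examples.

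The unaddressed outcome can also arise with no true difference: PP passes and FAS fails in about 1% of trials with no failures, and in up to about 31% in the worst equal-arm case tried.

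It might also be inferred that the stated 80% power refers to PP. The synopsis ties 128 to subjects who complete the study. PP is a different group: it keeps stops after week 9 and removes eligibility failures and significant deviations. Equating 20% dropout with 20% leaving PP is an assumption made here.

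This is a cheap improvement, with loss of power as its downside.

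**What to change.** In Protocol 10.3.1 and SAP 4.9, state:

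> With area reduction scored as positive and the difference taken as tNPWT − PICO, non-inferiority is concluded only if the criterion is met in both the Per Protocol Population and the Full Analysis Set.

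Apply the same condition to the interim efficacy recommendation (Protocol 11, SAP 3.3), which names no analysis set, and to the permutation p-value if that fallback is used. Reconcile the sign of the percentage-change formula with the decision rule.

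In Protocol 11 and SAP 3.1, give the power of the two-set rule and its assumptions. With equal arms, 20% leaving PP and no carried-forward failures, it is about 79%, against about 81% for PP alone; about 82 per arm instead of 80 would bring it to 80%. Under assumed failure rates it is lower: about 73-74% with 5% per arm at no change, about 65% with 2% per arm at +75%, and about 50% with 5% per arm at +75%. Do not state that the 80% applies to PP.

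If the two-set rule is declined, add one sentence saying what is concluded when PP passes and FAS fails. No clinical stopping rule needs to change. The cost is wording in both documents plus the power loss.

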10.2 HANDLING OF MISSING AND INCOMPLETE DATA

The methods used to handle missing or incomplete data for the efficacy and safety measures is be detailed in the SAP.

CONFIDENTIAL DOCUMENT
This document contains confidential information, which is the property of Smith & Nephew, Inc. Do not copy, disclose, or circulate without written authorization from the appropriate Smith & Nephew personnel

10.3 EFFICACY ANALYSIS

10.3.1 Primary Efficacy

The primary endpoint of the study is the percentage change in target ulcer area over the 12-week treatment period and will be analyzed as follows. An initial linear regression model will contain covariates for treatment, center, wound type, baseline (defined as Study Visit 1) target ulcer area and duration of target ulcer. For purposes of the primary analysis, any centers with less than 10 subjects will be pooled. A forward selection procedure will be used for the addition of other baseline covariates with an F-value to attain a significance level of 0.1. Further baseline covariates to be assessed as part of this procedure include: subject age, body mass index, baseline ulcer depth, ABI and baseline level of exudate. The resulting primary analysis presented will correspond to the final model from the forward selection procedure. The results for the initial model will also be presented. For each of the effects in the initial and final model, the p-value, parameter estimate and corresponding 95.4% confidence interval will be presented.

Secondary subgroup analyses may be conducted as a result of the covariate analyses. Additionally, treatment will be fitted on its own in a further linear regression model. The potential for interactions, particularly treatment by center interactions will be examined by fitting the required interaction terms in addition to those effects in the final linear regression model from the forward selection procedure.

Non-inferiority will be concluded in each case if the upper bound of the 95.4% confidence interval for the parameter estimate relating to treatment covariate (coded as tNPWT – PICO) is less than ($<$) 12.5 which relates to the desired one-sided test at the 2.5% significance level after adjusting for the interim analysis.

If distributional and model assumptions relating to the above analysis do not hold, a permutation test will be used as a distribution free non-inferiority analysis. The sampling distribution of the test statistic will be estimated by re-randomization of treatments to each of the study subjects. At a minimum the completed re-randomization process will be repeated 2000 times. However, if 2000 replicates are found to be insufficient for the random variation in results of successive repeats to be reduced to an acceptable level, the number of replicates will be increased until such a point as consistent results are observed between successive repeats of the permutation tests.

Detailed stopping criteria can be found in the SAP. For purposes of the permutation analysis, to test against the null one-sided hypothesis of a difference greater than delta, the non-inferiority margin (delta=12.5%) will be added to, or subtracted from, the observed change in individual area measurement for those subjects that are re-randomized by the permutation test to the treatment which they were not randomized to during the trial. The resulting p-value will be derived as per usual bootstrapping techniques.

The primary analysis (detailed in the previous paragraphs) will be performed using the Per Protocol Population; the analysis will also be repeated using the Full Analysis Set. Differences in conclusions between the two analyses will be investigated. The ability to switch between non-inferiority and superiority will be considered only if both subject populations demonstrate non-inferiority.

Further details, including model assumptions and diagnostics to be examined are included in the study SAP.

The percentage change in ulcer area will be summarized by treatment and center (and overall). Further summaries will be produced separated by the covariates used in the final model.

10.3.2 Secondary Efficacy

The secondary efficacy variables include the percentage change in target ulcer depth and volume over the 12-week treatment period (the key secondary endpoints), the time (in days) to achieve complete target ulcer closure either by surgical intervention or secondary intention, the proportion of subjects that achieve complete target ulcer closure by surgical intervention or secondary intention, and the change in subject reported Quality of Life (QoL).

Percentage change in target ulcer depth and volume over the 12-week treatment period (Key Secondary)

The primary analysis and accompanying summaries relating to change in target ulcer area will be repeated separately for both the change in target ulcer depth and volume over the 12-week treatment period with a single exception. The initial models will include baseline ulcer depth and

CONFIDENTIAL DOCUMENT
This document contains confidential information, which is the property of Smith & Nephew, Inc. Do not copy, disclose, or circulate without written authorization from the appropriate Smith & Nephew personnel

volume respectively for the two key secondary objectives rather than baseline ulcer area as described in the primary analysis.

Proportion of subjects achieving confirmed target ulcer closure over the 12-week treatment period

The proportion of subjects achieving confirmed target ulcer closure, either by surgical intervention or secondary intention, over the 12-week treatment period will be analyzed as follows using the Full Analysis Set. An initial logistic regression model will contain covariates for treatment, center, wound type, baseline (defined as Study Visit 1) ulcer area and duration of ulcer. Pooling of centers with less than 10 subjects will be performed as described in the primary analysis. A forward selection procedure will be used for the addition of other baseline covariates with an F-value to attain a significance level of 0.1. Further baseline covariates to be assessed as part of this procedure include: subject age, body mass index, baseline ulcer depth, ABI and baseline level of exudate.

The resulting analysis presented will correspond to the final model from the forward selection procedure. The results for the initial model will also be presented. For each of the effects in the initial and final model, the p-value, odds-ratio and corresponding 95% confidence interval will be presented. Secondary subgroup analyses may be conducted as a result of the covariate analyses. Additionally, treatment will be fitted on its own in a further logistic regression model. In each case, the residuals will be examined for outliers using influence plots of diagnostic statistics; further details are included in the SAP.

Cross-tabulations of each of the covariates (continuous covariates will be categorized for purposes of the cross-tabulations) with treatment and closure, will be generated for each of the baseline covariates included in the final model.

The 95% confidence interval (unadjusted for all covariates) for the difference between treatments in percentage healed by 12 weeks will be generated along with the Chi-square test p-value using the Per Protocol Population.

Two separate sensitivity analyses will be performed to ensure that the efficacy findings are not reliant on assumptions made in either the analysis or derivations; the analysis for the proportion

CONFIDENTIAL DOCUMENT
This document contains confidential information, which is the property of Smith & Nephew, Inc. Do not copy, disclose, or circulate without written authorization from the appropriate Smith & Nephew personnel

of subjects achieving confirmed ulcer closure will be repeated with the following modifications using the Full Analysis Set only:

- 1) In cases where subjects had missing data over the confirmatory target ulcer closure period (1 week follow-up) and it is unknown whether the closure is confirmed, these will be imputed as: Confirmed Closure=No.
- 2) In cases where subjects withdraw from the study prior to the end of the 12-week treatment period (except in cases where the ulcer has closed), the following will be imputed: Confirmed Closure=Yes.

Time (days) to achieve confirmed target ulcer closure by surgical intervention or secondary intervention

A proportional hazards survival analysis will be applied to the time to achieve (confirmed) target ulcer closure using the Full Analysis Set. An initial proportional hazards model will include the covariates for treatment, center, wound type, baseline (defined as Study Visit 1) ulcer area and duration of ulcer. Pooling of centers with less than 10 subjects will be performed as described in the primary analysis. A forward selection procedure will be used for the addition of other baseline covariates with an F-value to attain a significance level of 0.1. Further baseline covariates to be assessed as part of this procedure include: subject age, body mass index, baseline ulcer depth, ABI and baseline level of exudate. The resulting analysis presented will correspond to the final model from the forward selection procedure. The results for the initial model will also be presented. For each of the effects in the initial and final model, the p-value, hazard-ratio and corresponding 95% confidence interval will be presented. Secondary subgroup analyses may be conducted as a result of the covariate analyses. Additionally, treatment will be fitted on its own in a further proportional hazards survival analysis.

Further details, including model assumptions and diagnostics to be examined are included in the study SAP. The preceding analysis will be repeated using the Per Protocol Population.

Kaplan-Meier plots will be presented by treatment and wound type, baseline ulcer area strata, ulcer duration (categorized) and also to represent all covariates with significant effects in the

final survival analysis model. Individual plots for multiple factors will be generated where appropriate.

In addition, a sensitivity analysis will be performed to ensure that the efficacy findings are not reliant on assumptions made in either the analysis or derivations. For purposes of the sensitivity analysis, the time to confirmed closure for those subjects discontinuing the treatment period prematurely, will be censored at the maximum possible duration of treatment under the study protocol (84 days), rather than time of actual discontinuation. Lastly, the two sensitivity analyses defined in the proportion of subjects achieving confirmed closure analysis will be repeated for the time to confirmed closure, in these cases the censoring flag may be modified as detailed previously, but the time in days will remain unchanged.

Change in subject reported Quality of Life (QoL)

The instruments used to assess subject reported Quality of Life will be the Cardiff Wound Impact Schedule (CWIS) and the EQ-5D.

The EQ-5D is a standardized measure of health status developed by the EuroQoL Group and provides a simple measure of general health. The EQ-5D descriptive system contains 5 dimensions: mobility, self-care, usual activities, pain/discomfort and anxiety/depression. The subject is asked to state each dimension on a scale comprising of 3 levels: no problems, some problems, or severe problems. Separately, the EQ-5D visual analog scale (EQ VAS) records the subject's self-rated health on a vertical, Visual Analog Scale (VAS). This information is used as a quantitative measure of health outcome.

In comparison, the CWIS is a measure designed to specifically assess the impact of lower limb chronic wounds on subject health-related quality of life (HRQoL) and activities of daily living (ADL). The CWIS contains four domains; Quality of life, Well-being, Physical symptoms and Daily Living (Experienced and Stressfulness of experience are two separate domains).

Both the EQ-5D and CWIS will be provided to all subjects participating in the study at the Randomization Study Visit 1 and at the End of Treatment period for completion. Missing and ambiguous values will be coded as per the relevant instrument documentation. All analyses relating to Quality of Life assessments will be performed using the Full Analysis Set.

Subject responses to individual questions at each assessment are ordinal variables and will be summarized by treatment and wound strata (and overall) using frequency distributions which will detail the number and percentage of subjects which fall into each category.

Subject responses to the EQ VAS scale and derived Time Trade-off (TTO) indexes and domain averages at each assessment are continuous variables and will be summarized by treatment and wound strata (and overall) using the following summary statistics: mean, median, standard deviation, minimum and maximum values, and number of observations.

The change in EQ VAS, derived TTO index and domain averages between the Randomization Visit and the End of Treatment period will also be summarized separately using the above continuous summary statistics. A Wilcoxon Rank-Sum test stratified by wound strata will be used to test for a difference in the change in EQ VAS between the two treatments. This analysis will be repeated separately for the change in TTO index and domain averages.

